### 9.3.2 Definition of Serious Adverse Event (SAE)

means an adverse medical event resulting in death, life-threatening, permanent or serious disability or loss of function, the need for hospitalization of the subject, or prolonged hospitalization after the subject has undergone radical lung cancer surgery. A serious adverse event (SAE) is defined as an adverse medical event resulting in death, life-threatening, permanent or serious disability or loss of function, hospitalization or prolonged hospitalization after radical lung cancer surgery.

### 9.3.3 Classification of adverse events

#### 9.3.3.1 Severity of the incident

- 1) Mild: Symptoms and signs are easily tolerated by the patient. Symptoms may be ignored or disappear when the patient is distracted.
- 2) Moderate: Symptoms cause discomfort but are tolerable. They cannot be ignored and interfere with concentration.
- 3) Severe: Symptoms interfere with daily activities.

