### 2.2 Background

For operable early lung cancer, sub-lobe resection has been demonstrated to achieve similar oncologic outcomes compared with lobectomy [2, 3], while preserving the lung function. Pneumonectomy remains the standard surgical procedure for patients whose surgical strategies are pneumonectomy initially, although tumor downstaging after neoadjuvant therapy. More evidence is needed to determine whether the extent of surgical resection can be reduced for these patients.

Although pneumonectomy ensures a good R0 clearance rate, it is associated with a higher rate of perioperative complications and mortality than lobectomy. 355 patients with pneumonectomy were retrospectively analyzed by Gregory D. Jones' team [4], and the mortality rates were 3.7%, 4.5%, and 6.8% at in-hospital, 30 days, and 90 days, respectively, for non-oncological causes. 30- and 90-day readmission rates were 13% and 19%, respectively. The rate of readmission within 30 and 90 days was 13% versus 19%, with cardiopulmonary complications being the most common cause. In retrospective studies [5-8], the 30-day complication and mortality rates for total lung resection were 30% and 5%-8%, compared with 4%-10% and 0%-3% for lobectomy. In addition, the 90-day mortality rate after total lung resection can be 1-2 times higher than the 30-day mortality rate [9-10]. A controlled study published in the Annals of Surgery in 2022 [11] compared postoperative

complications and mortality rates between pneumonectomy and lobectomy by propensity score matching, and showed that the complication rates of grade III or higher and mortality at 90 days were significantly higher in the group of pneumonectomy than lobectomy (21% vs. 13% and 6.9% vs. 1.9%, respectively). The three complications with the highest rates were hypoxic respiratory failure, bronchopleural fistula, and intrathoracic hemorrhage. In addition, cardiovascular complications were significantly higher in the pneumonectomy group.

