#### Secondary study endpoints

- 1) Lymph node dissection: Record the total number of lymph node dissection, the number of stations of lymph node dissection, and the number of lymph node dissection at each station during the operation, and evaluate them according to the pathologic results.
- 2) Perioperative indicators: Record the duration of surgery, intraoperative bleeding, the incidence of intraoperative accidents, evaluated by surgical records and perioperative clinical manifestations, laboratory tests, physical examination;
- 3) Postoperative short-term efficacy indicators: record the length of postoperative hospitalization (days), survival within 30 days after surgery, and evaluate through postoperative follow-up;
- 4) Perioperative complication rate: Evaluated by clinical manifestations, laboratory tests, and physical examination.
- 5) 3-year disease-free survival rate: defined as the proportion of patients without tumor recurrence or metastasis 3 years after surgery, evaluated by postoperative follow-up.
- 6) 3-year overall survival rate: defined as the proportion of patients who are still alive 3 years after surgery, and evaluated by postoperative follow-up.

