## 9.3 Adverse Events and Serious Adverse Events

### 9.3.1 Definition of Adverse Events (AE)

This refers to all adverse medical events that occur after a subject has undergone radical lung cancer surgery, which may be manifested by signs, symptoms, disease, or abnormal laboratory tests, but are not necessarily causally related to the trial intervention.

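### Non-fatal surgical complications are graded only by symptom tolerance, and no planned result corresponds to the grade III or higher rates cited in the background

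*Protocol*

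**What the plan says.** Section 9.3.1 defines adverse events as "all adverse medical events that occur after a subject has undergone radical lung cancer surgery", including those seen only as signs or abnormal laboratory values. Section 9.3.3.1 then gives one severity scale for all of them:

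- "Mild: Symptoms and signs are easily tolerated by the patient"
- "Moderate: Symptoms cause discomfort but are tolerable"
- "Severe: Symptoms interfere with daily activities"

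No level stands above the third, and none is defined by re-intervention, organ support or death. Section 10.3 summarises adverse events by severity, so this scale feeds the safety analysis.

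The complication endpoints use no scale. Section 5.2 lists complication and mortality rates for the perioperative period and at 30 and 90 days. Section 9.1 says only "Perioperative complication rate: Evaluated by clinical manifestations, laboratory tests, and physical examination". Section 10.2 treats the rates as counts, compared between two groups by chi-square, with no severity threshold.

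Section 2.2 cites a propensity-matched comparison in which "complication rates of grade III or higher and mortality at 90 days were significantly higher in the group of pneumonectomy than lobectomy". The figures it gives are 21% against 13% for complications, and 6.9% against 1.9% for deaths.

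**The concern.** Symptom tolerance is a weak measure of how grave a surgical complication is. Section 2.2 names respiratory failure, bronchopleural fistula and bleeding inside the chest as the leading complications in its matched comparison, and 2.4.1 lists bleeding and air leak among the known risks. What makes such events serious is the physiological threat and the treatment required. Read literally, 9.3.3.1 puts activity-limiting wound pain in the same top level as a catastrophic bleed. An event seen only in a laboratory value has no symptom by which to place it.

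This matters because fewer perioperative complications are one of the claimed benefits of conversion (2.4.2). The study has a single arm (5.1), so a reader will naturally set its complication results beside published rates. For one of the benchmarks that the protocol cites, graded complications, the plan produces nothing of the same kind.

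**Working it through.** The protocol computes no figure on this point, and 5.3 states that the sample of 50 was not derived from a hypothesis test. The check is therefore a comparison of sections, followed by a precision calculation for the proposed result.

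**Step 1: what each benchmark in 2.2 needs, and what the plan yields.**

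| Benchmark in 2.2 (pneumonectomy vs lobectomy) | Matching planned result |
|---|---|
| Complications of grade III or higher, 21% vs 13% | None: 5.2, 9.1 and 10.2 have no grade, and 9.3.3.1 has no rule linking its levels to grade III |
| 90-day mortality, 6.9% vs 1.9% | Yes: 90-day mortality (5.2) |
| 30-day mortality, 5%-8% vs 0%-3% | Yes: 30-day mortality (5.2) |
| 30-day complications, no grade stated, 30% vs 4%-10% | Yes, in form: 30-day complication rate (5.2) |

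Only the first row fails.

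**Step 2: does the seriousness definition fill the gap?** Section 9.3.2 counts death and life-threatening events as serious, but also any admission or prolonged stay. It is a yes/no flag and does not give a grade.

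**Step 3: what a graded rate could show.** Inputs: n = 50 (5.3), taken as the denominator by assumption; benchmarks 13% and 21% (2.2). The exact (Clopper-Pearson) 95% limits for x events are:

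- lower = the 0.025 quantile of Beta(x, n - x + 1)
- upper = the 0.975 quantile of Beta(x + 1, n - x)

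For x = 6, the lower limit comes from Beta(6, 45) and is 4.5%. The upper limit comes from Beta(7, 44) and is 24.3%.

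| Events | Rate | Exact 95% CI | Contains 13% | Contains 21% |
|---|---|---|---|---|
| 3/50 | 6% | 1.3%-16.5% | yes | no |
| 5/50 | 10% | 3.3%-21.8% | yes | yes |
| 6/50 | 12% | 4.5%-24.3% | yes | yes |
| 7/50 | 14% | 5.8%-26.7% | yes | yes |
| 11/50 | 22% | 11.5%-36.0% | yes | yes |
| 15/50 | 30% | 17.9%-44.6% | no | yes |

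At observed rates near either benchmark, the interval covers both. Section 7.1.1 still allows pneumonectomy after reassessment, so the converted group may be smaller than 50 and its interval wider at the same rate.

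**The case against.** The strongest reply is that little is lost.

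- **Data collected.** Sections 9.3.5 and 9.3.6 include the action taken for each event among the reported items, and 9.3.4 asks for a description. A treatment-based grade could partly be assigned afterwards. This stands, so it would be wrong to say that grades could never be recovered. But no rule provides for it, and 9.3.4 asks for severity only as the physician's assessment. Grading at the time of the event is more reliable than reconstruction.
- **Deaths and life-threatening events.** A reader might infer from the missing top levels that these go unrecorded. They do not: 9.3.2 captures them as serious events and 5.2 makes mortality an endpoint. Keeping severity separate from seriousness is conventional.
- **Other references.** A reader might infer that the trial has no usable historical comparator, or that its case rests on the grade III figure. Neither is supported. Section 2.2 also gives mortality rates and 30-day complication rates, and the rationale includes non-cancer death, physical strength, quality of life and access to adjuvant treatment.
- **Spread of the lobectomy rates.** Setting 4%-10% against 13% does not demonstrate a grading problem. The cohorts differ, the first range is a 30-day figure, and several of the cited titles speak of major morbidity or major adverse events. The document does not call that range all-grade.
- **Precision and matching.** With at most 50 patients, grading would not settle whether morbidity resembles lobectomy or pneumonectomy. Section 2.2 also does not name the system behind grade III. Both points stand and limit what the fix can deliver.
- **Left to the analysis plan.** A separate plan could set the reporting. It cannot ensure that a grade is collected prospectively on the case report form.

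**Conclusion.** The point holds as a cheap improvement to a secondary outcome. The protocol states a severity scale ill-suited to surgical complications, leaves its complication endpoints ungraded, and so plans no result that corresponds to the 21% and 13% cited in 2.2. The defect is confined to the severity of non-fatal complications. The primary endpoint, the mortality endpoints and the recording of serious events are unaffected, and no formal comparison with published rates is planned.

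The conclusion rests on three assumptions: no complication grading is specified elsewhere, for example in the case report form, which is not shown; the 90-day horizon in the sentence in 2.2 applies to the complication rates as well as to mortality; and, for the intervals, the denominator is all 50 patients, which gives the best precision available.

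**What to change.** In 9.1 and 9.3.3.1, name one treatment-based surgical complication scale that runs up to death, and apply it prospectively on the case report form to complications in the perioperative period and to 30 and 90 days. Clavien-Dindo is one example; first check which system the cited grade III benchmark used, since comparability depends on that. The symptom scale can stay for non-surgical events.

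In 10.2, report the 90-day grade III or higher rate with an exact 95% confidence interval beside the overall complication rate. State the denominator, and state that with at most 50 patients the interval is wide and the comparison with published rates is descriptive only.

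The cost is one extra field on the case report form, a short coding instruction, and a little more effort per event from staff who already record complications.

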#### 9.3.3.2 Relevance to research interventions

- 1) Unrelated: A condition that occurs in a subject that is clearly related to other factors such as the subject's clinical status, treatment, or concomitant medications.
- 2) Unlikely to be related: What happens to the subject is likely to be caused by other factors such as the subject's clinical condition, treatment, or concomitant medications, but not by a known response to the intervention.
- 3) Possibly Related: What happens to the subject is sometimes related to the intervention or is a known response, but may also result from other factors such as the subject's clinical condition, treatment, or concomitant medications.
- 4) Likely Related: The subject has a condition that is sometimes related to the intervention, is a known response, and cannot be explained by other factors such as the subject's clinical status, treatment, or concomitant medications.
- 5) Highly Likely to be Relevant: The subject is experiencing a condition that is sometimes

related to the intervention, is a known response, and cannot be explained by other factors such as the subject's clinical status, treatment, or concomitant medications. There may also be one or more of the following: i) immediate onset after the intervention; ii) improvement after discontinuation of the intervention; iii) reoccurrence after a second intervention; iv) a positive reaction at the site of the intervention.

### **9.3.3.3 Anticipation**

Investigators should confirm that adverse events are expected or unanticipated, and that adverse events may be considered unanticipated if their nature, severity, or frequency are not consistent with the risk information described for previous study interventions, they may be considered unintended.

### **9.3.4 Timing, frequency, follow-up and regression of adverse event assessment**

Time and frequency of adverse event assessment: assessed every three days during hospitalization, and once at each follow-up visit after discharge.

Follow-up of adverse events: The investigator should follow up the adverse events; observe the final regression until the symptoms disappear or stabilize; the investigator should follow up the results with the principal investigator and the ethics committee.

All adverse events should be collected on a case report form (CRF), which should include a description of the event, time of occurrence, physician's assessment of severity, relationship to the study intervention, and time to resolution/stabilization of the event.

### **9.3.5 Adverse event reporting**

Adverse events should be promptly recorded on the Case Report Form (CRF) and regularly reported to the Principal Investigator, Ethics Committee:

- 1) description of the adverse event; and
- 2) the time of occurrence and duration; and
- 3) Whether the adverse event was serious or unintended.
- 4) the mode of onset; and
- 5) evaluation of severity; and
- 6) regression; and
- 7) Measures taken in response to the adverse event.

### **9.3.6 Reporting of Serious Adverse Events**

Serious adverse events should be promptly documented on a Case Report Form (CRF) and reported within 24 hours to the Principal Investigator, Ethics Committee.

- 1) the description of the adverse event;
- 2) time of occurrence and duration;
- 3) whether the adverse event was serious or unintended;
- 4) mode of onset;
- 5) assessment of severity;
- 6) regression;

7)Measures taken in response to the adverse event.

## 10. Statistical analysis

### 10.1 General methodology

All statistical analyses were performed using R software, and hypothesis tests were standardized using two-sided tests, giving the test statistic and its corresponding p-value.  $p<0.05$  was considered statistically significant, and 95% confidence intervals were set as required.

Statistical description: All indicators are described according to their nature. Qualitative indicators are expressed as frequencies and percentages of categories; metrics provide the number of cases, mean, standard deviation, median, minimum and maximum values.

Statistical inference: For overall survival time and disease-free survival time, overall survival curves and disease-free survival curves were plotted using the Kaplan-Meier method; risk differences between survival and disease-free survival were assessed using the Log-Rank test; multivariate analyses were performed using the Cox proportional risk model to assess the effect of subgrouping (surgical modality) and other prognostic factors on survival and disease-free survival. survival and disease-free survival. The t-test was used for measures that were normally distributed, and the rank-sum test was used for measures that were not normally distributed; the chi-square test was used for between-group comparisons of count data, and the Fisher exact probability method was used when necessary.

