### **5.3 Determination of sample size**

This study is a prospective observational clinical study, and the purpose of the study is to evaluate the feasibility and long-term outcome of pneumonectomy to lobectomy after neoadjuvant or induction chemoimmunotherapy for locally progressive non-small cell lung cancer. Due to the lack of previous reference data, the sample size was not calculated based on hypothesis testing, and 50 patients were enrolled.

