### 10.2 Analysis of Primary and Secondary Study Endpoints

#### Primary Endpoints

Overall survival time (in months): Overall survival curves were plotted using the Kaplan-Meier method; the difference in survival risk between the two groups was assessed using the Log-Rank test with 95% confidence intervals; multivariate analyses were performed using the Cox proportional risk model to assess the effect of subgrouping (surgical procedure) and other prognostic factors on the survival risk, and 95% confidence intervals were given for each factor. A multivariate analysis using the Cox proportional risk model was performed to assess the effect of grouping factors (surgical modality) and other prognostic factors on survival risk with 95% confidence intervals for each factor.

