#### Secondary endpoints

Disease-free survival time (in months): Disease-free survival curves were plotted using the Kaplan-Meier method; differences in the risk of disease-free survival between the two groups were assessed using the Log-Rank test with 95% confidence intervals; multivariate analyses were performed using the Cox proportional risk model to assess the effect of subgrouping factors (surgical procedure) and other prognostic factors on the risk of disease-free survival, with 95% confidence intervals for each factor. A multivariate analysis using the Cox proportional risk model was performed to assess the effect of grouping factors (surgical modality) and other prognostic factors on the risk of disease-free survival with 95% confidence intervals for each factor.

- Surgical evaluation indicators.
- Surgical time (unit: minutes), intraoperative bleeding (unit: ml), intraoperative blood transfusion (unit: ml): all quantitative data not conforming to normal distribution, calculate the median, 25% quartile, 75% quartile, the minimum value, the maximum value, and analyze the difference between the two groups by using the rank sum test.
- Incidence of intraoperative accidents: count data, using chi-square test to analyze the difference between the two groups.
- Lymph node dissection: the total number of lymph node dissection (unit: one) and the number of lymph node dissection at each station (unit: one) were non-normally distributed measurements, and the difference between the two groups was analyzed using the rank-sum test; the number of stations of lymph node dissection (intrapulmonary, hilar, and ipsilateral mediastinal lymph nodes) was count data, and the difference between the two groups was analyzed using the chi-square test. Differences between the two groups were analyzed using the chi-square test.
- Tumor R0 resection rate: count data, using the chi-square test to analyze the difference between the two groups.
- Perioperative, 30-day, and 90-day complication rates, and mortality rates: were count data, and differences between the two groups were analyzed using the chi-square test.
- Quality of Survival and Cardiorespiratory Function Evaluation at Admission, Discharge, 30 Days, and 90 Days
- Quality of Life Score SF-36 Scale: Percentage, as a non-normally distributed measure, use rank sum test to analyze the difference between the two groups.

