- Resting oxygen saturation (in percent): a non-normally distributed measure, differences between the two groups were analyzed using the rank-sum test.
- 

Lung function: Tidal volume, Vital capacity, Forced vital capacity, Forced Expiratory Volume In 1s, all in ml: were normally distributed measures and analyzed using the student The differences between the two groups were analyzed using the student-t test with 95% confidence intervals.

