### 10.5 Subgroup analysis

For the primary study endpoints grouped by age, sex or other demographic,

clinicopathologic characteristics, and surgical treatment modalities, a Subgroup analysis was performed.

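### Section 10.1 calls every two-sided p<0.05 statistically significant, and 10.2 applies this to about 22 to 42 between-group tests in a single-arm study not sized for testing

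*Protocol*

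**What the plan says.** Protocol section 10.1 prescribes that "hypothesis tests were standardized using two-sided tests, giving the test statistic and its corresponding p-value", and p<0.05 "was considered statistically significant, and 95% confidence intervals were set as required". No endpoint is exempt from this rule.

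Section 10.2 goes through the endpoints and gives each a comparison of two groups:
- Overall survival, under the primary heading: "the difference in survival risk between the two groups was assessed using the Log-Rank test with 95% confidence intervals". Disease-free survival is handled the same way under the secondary heading.
- Operative measures, node counts and the R0 rate: rank-sum or chi-square tests.
- Complications and deaths in three windows: "Perioperative, 30-day, and 90-day complication rates, and mortality rates: were count data, and differences between the two groups were analyzed using the chi-square test".
- SF-36, oxygen saturation and four lung-function measures, under the heading "Quality of Survival and Cardiorespiratory Function Evaluation at Admission, Discharge, 30 Days, and 90 Days". For lung function, "The differences between the two groups were analyzed using the student-t test with 95% confidence intervals".

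Section 10.5 adds subgroup analyses: "For the primary study endpoints grouped by age, sex or other demographic", followed by clinicopathologic characteristics and surgical modality.

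On sample size, section 5.3 states that "the sample size was not calculated based on hypothesis testing, and 50 patients were enrolled". Sections 5.1, 6.4 and 7.3 describe a single-arm study without allocation. Sections 5.2 and 9.1 name R0 resection by lobectomy as the primary endpoint.

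**The concern.** A blanket significance rule suits a trial with a hypothesis, a sample size built on it and a defined comparison. By its own account this protocol has none of these, yet section 10 attaches a verdict of significant or not significant to every comparison. It has no testing order, no key secondary endpoint, no key time point and no statement that the p-values are nominal.

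Sections 2.4.2 (benefits, and the risk/benefit assessment) anticipate fewer complications and deaths, preserved lung function and better physical status after conversion to lobectomy. Most of these outcomes are tested repeatedly: complications and mortality in three overlapping windows, lung function at four times on four measures. Followed as written, the plan would let one chance difference at one time point be reported as a statistically significant benefit of conversion.

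**Working it through.** The protocol states no number of tests and no family-wise error rate, and N = 50 has no formula behind it. There is therefore no figure of its own to reproduce. The count below is a reading of section 10.2.

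**Inputs from the protocol:** two-sided 0.05 per test (10.1); the endpoints, windows and time points of 10.2. **Assumptions:** the number of node stations tested, one test per listed time point, and all correlations.

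**Count**

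| Item in 10.2 | High count | Low count |
|---|---|---|
| Overall survival (log-rank) | 1 | 1 |
| Disease-free survival (log-rank) | 1 | 1 |
| Operating time, bleeding, transfusion | 3 | 3 |
| Intraoperative accidents | 1 | 1 |
| Total nodes | 1 | 1 |
| Nodes per station | 3 | 1 |
| Number of stations | 1 | 1 |
| R0 rate | 1 | 1 |
| Complications, three windows | 3 | 3 |
| Mortality, three windows | 3 | 3 |
| SF-36 | 4 | 1 |
| Oxygen saturation | 4 | 1 |
| Lung function, four measures | 4 × 4 = 16 | 4 |
| **Total** | **42** | **22** |

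Six of the 42 are admission comparisons (SF-36 1, oxygen saturation 1, lung function 4). They are baseline values, so they cannot show an effect of surgery. Without them the count is 42 − 6 = 36. Cox model p-values and subgroup analyses are not counted.

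**Chance of at least one false positive, all nulls true**

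Under independence the formula is 1 − 0.95^k:
- k = 22: 1 − 0.95^22 = 0.68
- k = 36: 1 − 0.95^36 = 0.84
- k = 42: 1 − 0.95^42 = 0.88

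The endpoints overlap and are measured in the same patients, so independence is unrealistic. With equally correlated normal test statistics (each |z| > 1.96 counted as positive):

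| Tests | Correlation 0 | 0.5 | 0.8 | 0.9 |
|---|---|---|---|---|
| 22 | 68% | 44% | 23% | 16% |
| 36 | 84% | 55% | 27% | 18% |
| 42 | 88% | 58% | 28% | 19% |

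The smallest count with the strongest correlation still gives 16%, about three times the nominal 5%.

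**Expected number of false positives** is 0.05k whatever the correlation: 1.1 for 22 tests, 1.8 for 36 and 2.1 for 42.

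**Direction of error.** Chi-square or Fisher tests on rare events such as deaths reject less often than 5%, and some nulls may be false. Both lower these figures.

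**The case against.** The strongest reply is that a protocol commonly leaves multiplicity and the labelling of p-values to the statistical analysis plan, which is not at hand. The p<0.05 convention could also be standard wording that promises no claim. Section 2.2 says the study is meant to explore, section 5.3 calls it observational, and the expected benefits in 2.4.2 are largely hedged. This stands in part: the absence of an alpha adjustment is no fault by itself. But 10.1 is not silent. It states a significance rule for all tests, and that rule conflicts with 5.3. The exploratory intent is never carried into section 10.

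A second reply is that the two groups are the deeper problem. The study is single-arm, and 10.2 identifies the groups only by surgical modality. That is correct, and it means the tests are not fully specified. Defining the groups would still leave every test under the same rule.

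Several stronger readings are tempting but not supported:
- **No hierarchy at all.** Primary and secondary tiers exist in 5.2, 9.1 and 10.2. What is missing is a testing order, and the tiers disagree: R0 is primary in 5.2 and 9.1, while 10.2 heads overall survival as primary and lists R0 among the secondaries.
- **Unlimited subgroup testing of everything.** Section 10.5 covers only the primary endpoints and states no test or p-value. Its factor list is open-ended, but no error rate can be computed for it.
- **An 88% error rate as a property of the plan.** That needs the highest count, independence and every null true. The background in 2.2 itself cites differences between pneumonectomy and lobectomy, so some nulls may well be false.

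**Conclusion.** The point holds as a mismatch between a stated decision rule and the stated design. About 22 to 42 between-group comparisons are each to be called significant at p<0.05, in 50 patients not sized for testing and with no comparison arm. If all nulls were true, at least one false positive would occur with probability of about 68% to 88% under independence and about 44% to 58% at correlation 0.5. The counts are readings of 10.2, the correlations are assumed, and the figures are upper ones.

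A reader might infer that the protocol needs a Bonferroni or similar adjustment. The documents do not support that. The study makes no confirmatory claim that requires family-wise control, and formal adjustment of secondary comparisons would be a trade-off for the sponsor. The remedy that fits is to state that these comparisons are exploratory. It is a cheap improvement that changes what the trial may conclude.

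**What to change.** **Section 10.1.** State that all between-group comparisons by surgical modality in 10.2 are exploratory, including the log-rank and Cox analyses of overall and disease-free survival and the R0 comparison, as are all subgroup analyses in 10.5. They are reported as estimates with 95% confidence intervals, and any p-values are nominal. No claim of statistical significance, or of benefit from conversion, rests on them.

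**Section 10.2.** Keep R0 resection by lobectomy, the primary endpoint in 5.2 and 9.1, as the single primary analysis, reported as a proportion with its 95% confidence interval. Reconcile the headings so that overall survival is no longer shown as primary and R0 no longer as secondary. The exploratory label has to name the analyses, as above. If it covered only those headed secondary, the current headings would make R0 exploratory and leave the overall survival test under the p<0.05 rule.

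**Section 10.5.** Replace the open-ended wording with a short named list drawn from the categories already given (age, sex, clinicopathologic characteristics, surgical modality), labelled exploratory.

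**Cost.** Wording only, with no extra patients or data. The price is that isolated p<0.05 results can no longer be presented as significant findings.
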